Interim results from Study CP0001¹⁶ have shown that AC220 has been well tolerated in the 76 patients treated thus far. The majority of adverse events (AEs) observed in the study were those associated with the underlying disease. In addition, the safety profile was similar between patients receiving continuous dosing (28 days continuous dosing as 1 cycle) and those on the intermittent schedule (14 days dosing and 14 days rest as 1 cycle). In spite of limitations of the Phase 1 design, e.g., limited evaluation of response and the potentially suboptimal intermittent dosing schedule, encouraging preliminary evidence of clinical activity has been observed in the first 76 patients treated with AC220. The overall response (complete remission [CR] + partial remission [PR]) observed in all AC220-treated patients was 32% (24/76). Responses were defined per modified Cheson criteria.¹⁷ Ten patients achieved a CR defined as a decrease of $< 5\%$ blast in bone marrow: 2 complete hematological recovery, 4 with incomplete platelet recovery (CRp), and 4 with incomplete platelet and neutrophil recovery (CRi). One of these patients also had complete resolution of leukemia cutis. Fourteen patients had PR, defined as a decrease of $\geq 50\%$ blasts to levels of 5% to 25% in the bone marrow but with incomplete peripheral recovery of neutrophils and platelets. Most of the patients had best bone marrow responses (14/22, 64%) during the first 28 days of treatment (defined as Cycle 1). Median duration of response was 14.1 weeks (range, 4 to 61+ weeks). Consistent with the proposed mechanism of action, the response in the FLT3-ITD mutant population was the highest with an overall response rate of 61% (11/18) including 6 PR, 3 CRi, 1 CRp, and 1 CR.

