During the two decades between the start of the CALGB studies and the approval of 5-azacytidine, a new understanding of MDS has developed, such as the World Health Organization (WHO) diagnostic criteria, the International Prognostic Scoring System (IPSS), and the International Working Group (IWG) response criteria. Silverman et al. reevaluated the combined data (N = 309) from 3 of the CALGB studies using the WHO classification system for MDS and AML and the IWG response criteria.⁴⁵ Using the IWG response criteria in MDS patients, response rates were between 40% and 70% in 5-azacytidine treated patients. Ten to 17% of patients achieved a complete remission; partial remission was rare; and 23% to 36% of patients had a hematologic improvement. In patients with AML (N = 103), 35% to 48% had hematologic improvement or better responses. The median survival time for 27 patients assigned to 5-azacytidine was 19.3 months compared with 12.9 months for the 25 patients assigned to observation.⁴⁵

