We hypothesize that adding AC220 to a hypomethylating agent such as AZA or to standard chemotherapy such as cytarabine may improve the response rate expected from the use of either agent alone. In the first portion of this study, we propose to explore the proper dose for these combinations and will explore this in patients with refractory or relapsed AML or MDS. Once the dose finding study is completed we will take this approach to a frontline or first salvage setting. Furthermore, in the phase 2 study of AC220 as single agent in patients with refractory or relapsed AML without FLT3 mutations, a response rate of 30% to 36% was reported in older patients receiving first salvage, or patients of any age receiving second salvage. This is a very significant response rate achieved with a single agent, well-tolerated agent, not regularly achieved with other standard or investigational agents. Despite a high response rate for this setting with a single-agent oral agent, the use of AC220 in this subset of patients has not been further explored clinically. We hypothesize that the combination of AC220 and azacytidine may result in a higher response rate and may offer a valuable salvage strategy to this patient population.

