10.2 Response Criteria for AML

Response criteria will be modified from the International Working Group for AML (JCO 2003; 21: 4642-9). Responders are patients who obtain a CR, CRi, or PR, with or without cytogenetic response, hematologic improvements, and morphologic leukemia-free state. Briefly, criteria are as follows:

10.2.1 Complete remission (CR):

- ◆ **Peripheral blood counts:**
No circulating blasts
Neutrophil count $\geq 1.0 \times 10^9/L$
Platelet count $\geq 100 \times 10^9/L$
- ◆ **Bone marrow aspirate and biopsy:**
 $\leq 5\%$ blasts
No Auer rods
No extramedullary leukemia

10.2.2 Complete remission with incomplete blood count recovery (CRi):

- ◆ **Peripheral blood counts:**
No circulating blasts
Neutrophil count $< 1.0 \times 10^9/L$, and/or
Platelet count $< 100 \times 10^9/L$
- ◆ **Bone marrow aspirate and biopsy:**
 $\leq 5\%$ blasts

No Auer rods
No extramedullary leukemia

10.2.3 Partial remission:

- ◆ All CR criteria if abnormal before treatment except:
- ◆ $\geq 50\%$ reduction in bone marrow blast but still $> 5\%$

10.2.4 Morphologic leukemia-free state:

- ◆ Bone marrow: $\leq 5\%$ myeloblasts

10.2.5 Hematologic Improvement (HI): Hematologic response must be described by the number of positively affected cell lines.

- ◆ **Erythroid response (E)** (pretreatment Hgb < 11 g/dL)
Hgb increase by ≥ 1.5 g/dL
- ◆ **Platelet response (P)** (pretreatment platelets $< 100 \times 10^9/L$)
Absolute increase of $\geq 30 \times 10^9/L$ for patients starting with $> 20 \times 10^9/L$ platelets
Increase from $< 20 \times 10^9/L$ to $> 20 \times 10^9/L$ and by at least 100%
- ◆ **Neutrophil response (N)** (pretreatment ANC $< 1.0 \times 10^9/L$)
At least 100% increase and an absolute increase $> 0.5 \times 10^9/L$
- ◆ **Blast response (BI)** a $\geq 50\%$ reduction in blast percentage in bone marrow and/or $\geq 50\%$ reduction in peripheral blood total blast count.

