12.3 Phase II

A: Cohort 2A – FLT3-ITD

The primary endpoint of the phase II portion of the study is overall response (CR+Cri+PR+HI) (first 2 treatment courses). It would be encouraging if the overall response rate reaches 50%.

Treatment with AC220 + low-dose cytarabine (Cohort 2A-FLT3-ITD)

Patients enrolled in the treatment of AC220 + low-dose cytarabine could be newly diagnosed or previously treated. A total of 26 patients (including 6 patients treated at MTD in Phase I) will be treated with this treatment combination. The toxicity and efficacy (CR+Cri+PR+HI) will be monitored during the study, and all the data will be used to update the prior distributions for toxicity and efficacy parameters. The study will be stopped for toxicity and futility based on the following stopping rules. If the trial for this treatment continues until 26 patients are evaluated, and assuming the overall response rate is 50%, then the 95% credible interval for overall response rate would be (0.32, 0.68).

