That is, the trial in one group will be stopped early for futility if the data for that group indicate that there is more than 98% probability that the response rate is less than 50% or the trial for one group will be stopped early for toxicity if the data that group indicate that there is more than 90% probability that the toxicity rate (i.e. DLT rate) is more than 30%.

The corresponding stopping boundaries for futility is: the trial in one group will be stopped early if (the number of response observed / among number of patients) in that group $\leq 3/15, 5/20, 7/25, 9/30, 11/35, 13/40$ and $15/45$.

The corresponding stopping boundaries for toxicity is: The trial will be stopped early in one group if (the number of patients experienced DLTs / among number of patients) in that group $\geq 8/15, 9/20, 11/25, 13/30, 15/35, 16/40$ and $18/45$.

Table 2 presents the operating characteristics for the above design.

Table 2: OCs for the design for cohort 2A with AC220 + 5-AZA

Response rate	Toxicity rate	Probability of early stopping	Average number of patients
0.2	0.1	0.993	18.6
	0.2	0.993	18.6

	0.3	0.994	18.2
	0.4	0.998	17.4
	0.5	1	16.2
0.35	0.1	0.584	35.8
	0.2	0.59	35.5
	0.3	0.669	32.9
	0.4	0.865	26
	0.5	0.983	19.4
0.5	0.1	0.055	48.6
	0.2	0.069	48.2
	0.3	0.247	43.7
	0.4	0.694	31.7
	0.5	0.96	21
0.65	0.1	0.009	50
	0.2	0.016	49.6
	0.3	0.204	44.8
	0.4	0.676	32.4
	0.5	0.958	21.2

If the trial in one group continues until 50 patients are evaluated, and assuming the overall response rate is 50%, then the 95% credible interval for overall response rate would be (0.36, 0.64).

B: Cohort 2B – FLT3-WT

Up to 50 patients FLT3-WT will be treated AC220 + 5-azacytidine. The primary objective is to determine the over response. In a recent phase 2 study, we observed a single agent AC220 response of 30% in a salvage setting. We would like to have a 15% improvement (i.e. response rate of 45%) under the combination treatment in this study.

The study will also monitor futility and safety for this cohort. Monitoring will begin when 15 patients have been enrolled in that group, and thereafter by a cohort of 5 patients. The trial in this cohort will be stopped early if at any time point the data in that group suggest

$$\Pr(P_E < 0.15 + P_S \mid \text{data}) > 0.98 \text{ or}$$

$$\Pr(\theta_E > 0.30 \mid \text{data}) > 0.9$$

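### Cohort 2B adds 15 points to a single-agent AC220 rate whose response definition and time window are not stated, so it is not shown to be the same endpoint as CR+CRi+PR+HI in two courses

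*Combined protocol and SAP*

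**What the plan says.** Section 12.3, part B (Cohort 2B, FLT3-WT) gives the aim as "The primary objective is to determine the over response" and the reference as "In a recent phase 2 study, we observed a single agent AC220 response of 30% in a salvage setting". The target is 45%. Accrual stops for futility when Pr(P_E < 0.15 + P_S | data) > 0.98, where P_E is the combination's response rate and P_S the standard rate.

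The Rationale for study describes the single-agent phase 2 experience in AML without FLT3 mutations as "a response rate of 30% to 36% was reported in older patients receiving first salvage, or patients of any age receiving second salvage". Neither place gives the response components or the assessment window.

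The endpoint is defined once, at the start of Section 12.3: "The primary endpoint of the phase II portion of the study is overall response (CR+Cri+PR+HI) (first 2 treatment courses". The sentence sits under the Cohort 2A heading but is worded for all of phase II, and part B offers no other definition. In AML, HI (Section 10.2.5) includes an improvement in a single cell line, or a fall of at least half in marrow or blood blasts.

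**The concern.** The rule subtracts one response rate from another. The difference can be read as a gain over AC220 alone only if both rates count the same events over the same time. P_E is broad in what it counts and limited to two courses; P_S is undefined on both.

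If the 30% excludes HI, some patients count toward the 45% target who would not have counted in the reference, and a combination with no real gain is less likely to be stopped. If the 30% is a best response at any time, the two-course limit lowers P_E relative to it, and a combination with the hoped-for gain is more likely to be stopped. Either way, the difference mixes drug effect with definition.

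**Working it through.** **1. Reproduce the plan's figures.** Inputs from Section 12.3 B: P_E ~ beta(0.6, 1.4), cut-off 0.98, looks at 15, 20, …, 45, maximum 50. P_S has no stated prior, so take it as fixed at 0.30. The boundary at n is the largest x with Pr(P_E < 0.45 | beta(0.6 + x, 1.4 + n − x)) > 0.98.

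- At n = 15 the probability is 0.9835 for x = 3 and 0.9433 for x = 4, so the boundary is 3.
- At n = 45 it is 0.989 for x = 13 and 0.976 for x = 14, so the boundary is 13.
- All seven looks give 3, 4, 6, 8, 10, 11, 13, as printed.

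An exact binomial recursion over the looks, with the printed toxicity boundaries and toxicity independent of response, reproduces all nine rows of Table 3. At toxicity 0.1:

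| True rate | P(early stop): computed / printed | Average N: computed / printed |
|---|---|---|
| 0.30 | 0.645 / 0.64 | 33.0 / 33 |
| 0.45 | 0.080 / 0.08 | 47.8 / 47.8 |
| 0.60 | 0.002 / 0.002 | 49.9 / 49.9 |

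The arithmetic is sound. The open question is what the 0.30 and the 0.45 measure.

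**2. Set the definitions side by side.**

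- *Phase 1 study (Section 2.1):* "The overall response (complete remission [CR] + partial remission [PR]) observed in all AC220-treated patients was 32% (24/76"). CR there includes CRp and CRi. The 14 PRs were marrow blast falls of at least 50% to a level of 5% to 25%, "in the bone marrow but with incomplete peripheral recovery of neutrophils and platelets". HI is not counted.
- *Randomized two-dose trial (Section 2.4):* the overall rate is CRc + PR (47% + 24% = 71% at 60 mg; 47% + 13% = 60%, printed as 61%, at 30 mg), tabulated as best response. HI is not counted.
- *This trial (Section 10.2.3):* PR requires "All CR criteria if abnormal before treatment except" for a marrow blast reduction of at least 50% that still leaves more than 5%. It is therefore stricter on blood counts than the phase 1 PR.
- *This trial (Section 10.2.5):* a marrow blast fall of at least 50% is a blast response, and so counts as HI.

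A phase 1-type PR without count recovery therefore fails PR here but still enters P_E through HI. The excess of P_E over a CR+PR reference is limited to HI beyond that: improvement in a cell line alone, a blast fall in blood alone, or a marrow blast fall that leaves more than 25%. The documents do not give its size.

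**3. Illustrate the effect under assumed shifts.** Printed futility boundaries, toxicity 0.1.

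| Scenario (assumed) | Rate seen by the rule | P(early stop) |
|---|---|---|
| No gain, same definition | 0.30 | 0.645 |
| No gain, extra HI adds 5 points | 0.35 | 0.394 |
| No gain, extra HI adds 10 points | 0.40 | 0.195 |
| No gain, extra HI adds 15 points | 0.45 | 0.080 |
| True 45%, window lowers it to 40% | 0.40 | 0.195 |
| True 45%, window lowers it to 36% | 0.36 | 0.348 |

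**4. Check the matched alternative.** If reference and target both rise by 5, 10 or 15 points and the boundaries are recalculated, stopping for a combination with no gain returns to 0.584, 0.642 or 0.637.

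**The case against.** The strongest reply is that the documents never say the 30% excluded HI or was a best response. That stands. A reader might infer that the two endpoints are known to differ, but the breakdowns come from a phase 1 study and from a table whose randomized trial was in FLT3-mutated AML. The AC220-002 columns in that table sum to 72%, 73% and 92% for CRc + PR, so they are not the 30% result. The supported statement is that comparability is not shown, with exclusion of HI the likelier case.

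A reader might also infer that every HI responder inflates P_E with no counterpart in the reference. The definitions do not support this: 14 of the 24 phase 1 responders had the kind of PR that would enter here as a blast response.

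Section 10.2 defines responders as those with CR, CRi or PR, with or without hematologic improvement. On one reading HI alone is then not a response, and the HI part of the concern disappears. This conflicts with the endpoint sentence in Section 12.3 and is itself a reason to clarify.

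The shifts are assumptions. Section 2.2 reports for azacitidine in MDS that "partial remission was rare; and 23% to 36% of patients had a hematologic improvement", but for AML it gives only a combined figure of 35% to 48% for hematologic improvement or better. The phase 1 finding that 14 of 22 best marrow responses came in cycle 1 does not show how many came after course 2.

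Finally, 2B has a futility rule and a credible interval, not a hypothesis test, and Table 3 is indexed by the true rate on whatever endpoint is counted. Both points are right. What remains is that a 15-point improvement cannot be interpreted when the rate it is added to has no definition.

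**Conclusion.** The concern holds in a limited form. The 2B futility rule and the 45% target rest on a 30% reference with no stated components or window, set against an endpoint that counts HI within two courses. The 30% probably excludes HI, by inference from how the protocol reports other AC220 results. The direction of the net bias is unknown, because extra HI raises the observed rate and the two-course window may lower it.

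The possible size is not trivial. Assumed shifts of 5 to 15 points move early stopping for a combination with no gain from 0.645 to between 0.394 and 0.080. A window loss from 45% to 40% or 36% moves stopping from 0.080 to 0.195 or 0.348.

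A reader might conclude that the boundaries or Table 3 are wrong. They are not; both reproduce. This goes beyond a missing detail, because the plan as written lets improvement in a cell line alone, or a blast fall in blood alone, count toward a target set from a single-agent rate that probably did not count them.

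**What to change.** In Section 12.3 B:

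1. State the response components and time window of the 30% reference.
2. Reconcile the responder sentence in Section 10.2 with the endpoint sentence in Section 12.3 on whether HI alone is a response, and restate the endpoint for 2B.
3. Apply the P_S + 0.15 rule and the 45% target to responses scored by the reference's definition and window. Report the CR+CRi+PR+HI rate and the HI-only responders separately.

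If P_S is still 0.30 on that definition, the boundaries and Table 3 stand. They do not stand if P_S changes. For example, if 10% or 20% of reference responses came after course 2 (an assumption) and P_S were limited to two courses, P_S would be 0.30 × 0.9 = 0.27 or 0.30 × 0.8 = 0.24. The cut-offs would be 0.42 or 0.39, and the boundaries 2, 4, 5, 7, 9, 10, 12 or 2, 3, 5, 6, 8, 9, 11.

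The alternative is to re-derive P_S from the phase 2 data as CR+CRi+PR+HI in the first two courses and recalculate the boundaries and Table 3.

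The first route costs one paragraph and one extra tabulation. Its downside is that the rate compared with 45% may be lower than the HI-inclusive rate. The second needs access to the phase 2 patient data.

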13.0 PROTOCOL ADMINISTRATION

Protocol amendments

Changes to the protocol will be made only when protocol amendments have been signed by the principal investigator and approved by the sponsor and the IRB of the study center.

Archival of data

All patient data (including source data) generated in connection with this study will be kept in the archives of the MDACC for at least 15 years after the study has been completed. All data will be available for inspection by company representatives of the Medical Department and by regulatory authorities.

Appendix AA – Schedule of Events*

Assessment	Pre-Treatment Evaluation (procedures to be performed within 14 days prior to study drug administration except where indicated)	Cycle 1 and 2 - Day 1 (+/- 5 days), then every 2-3 cycles until end of Month 6	Once weekly during Cycles 1-3, then every 2-4 weeks until end of Month 6 (all ±2 days)	Cycle 1 Day 28 (+/- 7 days), then every 1-3 cycles until end of Month 6	Cycle 1-4, Days 1, 8, and 15 (all ±2 days)
Complete History ^a	X				
Physical Examination	X	X			
Concomitant Medications	X	X			
Performance Status	X				
CBC, Platelet Count, Differential ^b	X		X		
Serum Chemistry	X ^c		X ⁱ		
Urine or Serum Pregnancy Test (WCBP) ^d	X				
Bone Marrow Aspiration	X ^e			X	
FLT3 Evaluation ^f	X				
EKG, ECHO, and/or MUGA ^g	X				
Correlative Studies ^h	X				X
Drug Administration Diary		X ⁱ			
EKG		X ^k			

* For patients that remain on study with no significant toxicity for more than 6 months, subsequent evaluations during study may be modified after discussion with the principal investigator. These include a decrease in frequency of standard laboratory tests to once every cycle, bone marrow aspirations to every 6-12 months (or as clinically indicated).

^a documentation of all measureable disease

^b differential can be omitted if WBC is $\leq 0.5 \times 10^9/L$

^c creatinine, total bilirubin, ALT, potassium, magnesium, calcium, sodium, chloride, CO₂, uric acid, phosphorus, BUN

^d 48 hours before initiation of study

^e during the last 44-21 days preceding study initiation. Cytogenetics will be obtained prior to therapy (results from prior analysis can be used for this purpose)

^f if not done within 90 days, provided there has been no intervening therapy other than hydroxyurea or isolated single-agent doses of cytarabine.

^g before initiating study treatment if not done within 28 days

^h see Protocol Section 8.0

ⁱ drug administration of self-administered drugs (cytarabine and AC220)

^j creatinine, total bilirubin, ALT, K, Mg, Ca, sodium, chloride, and CO₂; on day 5 prior to start of AC220 and on day 6 [as clinically indicated](#)

^k EKG will be performed on day 1, day 5, day 8, and day 12 of the first cycle (all ± 2 days) Day 1 and day 8 ECG are collected pre-dose; day 5 are collected pre-dose and 4 hrs (+/- 2 hrs) post-dose; day 12 are collected 4 hrs (+/- 2 hrs) post-dose. Then ECG to be done on day 1 of each cycle for cycles 2 and 3 before initiation of quizartinib and 4 hr (+/-2 hrs) post dose, then pre-dose every 2-3 cycles. EKG may be omitted if patient has not received study drug (AC220) in the 48 hrs preceeding the time when EKG is done. EKG for the first 3 cycles will be done in triplicate. Day 5 pre AC-220 will be used as baseline.
